# 10 STUDY ADMINISTRATION PROCEDURES

## 10.1 SUBJECT ENTRY PROCEDURES

### 10.1.1 OVERVIEW OF ENTRY PROCEDURES

Prospective subjects as defined by the criteria in Section 5.3 and 5.4 (inclusion/exclusion criteria) will be considered for entry into this study.

### 10.1.2 INFORMED CONSENT AND SUBJECT PRIVACY

The purpose, procedures, risks, benefits, and alternatives to study participation will be discussed with each potential subject. Prior to any study-related procedures or change in treatment, subjects wishing to participate must give their written informed consent (IC). The subject must also give Authorization for Use and Release of Health and Research Study Information (HIPAA) and other written documentation in accordance with the relevant country and local privacy

requirements (where applicable) prior to any study-related assessments/questionnaires. Subjects will be consented to provide a copy of all medical imaging (e.g. radiology) collected as standard-of-care or research during the study duration for inclusion in the study file. The Investigator will conduct the IC discussion and will document in the subject's medical records the process for acquiring IC and the subject's agreement or refusal to notify her primary care physician about the study. The subject should personally sign and date the IC form. The Investigator will retain the original copy of the signed IC form, and the subject will also receive a copy. Upon signing the IC form, the subject will receive a subject number that will be used on all documentation for the subject throughout the study. Subject numbers should be assigned in ascending order, and numbers should not be omitted or reused. The subject number is a unique identification for each subject.

## 10.2 COMPLIANCE WITH PROTOCOL

All eligible subjects to be treated by [name] will be counseled on the procedure as well as the possibility of treatment with PRP, as dictated by their randomization to treatment with PRP versus normal saline. Eligible patients enrolled into each treatment arm will be asked to complete research questionnaires and post-operative assessments as indicated within the schedule or procedures. The Investigator is responsible for the overall conduct of the study and compliance with the protocol including subject recruitment, IC, screening evaluations, eligibility, assessment/procedure, study evaluations, and any study-related medical care. The Investigator may choose to delegate some of these tasks to suitably trained research staff personnel, but the Investigator is ultimately responsible for these activities.

## 10.3 STUDY TERMINATION

If conditions arise during the study that indicate that the study should be terminated, the Investigator, Monitor, IRB, and/or regulatory agencies will discuss the situation and take appropriate action after consultation. Conditions that may warrant termination of the study or site include, but are not limited to:

- Discovery of an unexpected, serious, or unacceptable risk to subjects enrolled in the study
- Failure of the Investigator to comply with pertinent national or state regulations, IRBimposed conditions, or protocol requirements
- Submission of knowingly false information from the Investigator to IRB, or any regulatory agency

## 11 ADVERSE EVENTS

Throughout the course of the study, AEs will be monitored and reported on an AE CRF, including seriousness, severity, relationship to device, and action taken. If AEs occur, the first concern will be the safety of the study participants. The Investigator and the research staff will monitor each subject closely, and record any complications that may arise, though not anticipated. Study clinician will use his/her medical judgment to do whatever is necessary to help treat the problem. Potential risks and/or side effects include:

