## 6.2 STANDARD OPERATIVE PROCEDURES

Standard Imaging: PA, lateral, and oblique X-ray views of the wrist and MR Arthrogram will be obtained pre-operatively and 6 months post-operatively. Medical photographs of the hand and wrist will be taken at each visit and on the day of the procedure.

Standard Surgical Procedure: The affected wrist is placed in a traction tower and arthroscopy is performed in standard fashion. A blunt trocar is placed through the 3/4 portal and a probe is used through the 4/5 portal. The wrist is then inspected for evidence of injury including the central and peripheral portions of the TFCC. An ArthroCare device is then inserted into the 4/5 portal, and the frayed TFCC is coblated.

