### 6.3 RESEARCH RELATED PROCEDURES

Research Related Procedures: Once the arthroscopic debridement is complete, the patient is randomized to receive wrist injections of normal saline (placebo) or PRP (treatment group). The PRP is then obtained from patients assigned to the treatment arm (~9 cc of venous blood) and processed using the CASCADE Autologous Platelet System, a product made commercially available by the Musculoskeletal Transplant Foundation (MTF). Once processed, the PRP is injected into the debrided wrist.

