### 9.3.4 SAFETY ANALYSIS

Safety analyses will include the incidence and severity of adverse events observed over the study assessment period. These will be tabulated and presented overall and by relatedness, severity, and preferred term.

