### 11.1 DEFINITIONS

#### 11.1.1 ADVERSE EVENT

An adverse event (AE) is any untoward medical occurrence in a subject that does not necessarily have a causal relationship with the treatment. An adverse event can therefore be any unfavorable and unintended sign (including an abnormal laboratory finding), symptom, or temporal disease, whether or not related to the study assessment(s)/questionnaire(s).

Pre-existing disease or symptoms thereof prior to study enrollment are not considered AEs unless the condition recurs after the subject has recovered from the pre-existing condition, or the condition worsens in intensity or frequency during the study. Normal post-operative sequelae will not be recorded as adverse events. Specifically, normal post-operative pain, swelling, tenderness, loss of skin sensation and ecchymosis within the first two weeks postoperative, requiring normal levels of medication will not be recorded; all abnormal intensity or duration will be recorded and considered an adverse event as well as following the two-week post-operative period.

Adverse events will be monitored throughout the study. At each post-baseline visit, the Investigator will begin querying for adverse events by asking each subject a general, nondirected question such as "Have you had any changes to your condition since your last visit?" Previous adverse events and changes in therapy/concomitant medications should be updated. Directed questioning and examination will then be done as appropriate. All reported adverse events will be documented.

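### Adverse-event causality is rated against an undefined device, so relatedness to the randomised injection cannot be rated reliably or on equal terms in both arms

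*Combined protocol and SAP*

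**What the plan says.** The randomised comparison is a wrist injection of PRP or of normal saline, given after debridement, with 24 subjects planned per arm (sections 5.1 and 6.3).

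For AEs, section 11 says the form will record events "including seriousness, severity, relationship to device, and action taken". Section 9.3.4 says they will be tabulated and "presented overall and by relatedness, severity, and preferred term". It does not say related to what, and treatment arm is not among the listed breakdowns.

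In the procedures of section 6 the word device occurs once, in section 6.2: "An ArthroCare device is then inserted into the 4/5 portal". The PRP is "processed using the CASCADE Autologous Platelet System" (section 6.3), which that section calls a system and a product. Section 12.3.3, on document retention, also uses the word, for something whose distribution and use are logged and whose clinical development might be stopped.

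Other sections speak of relatedness in other terms. Section 8.2 refers to AEs related to the study. Section 11.1.1 first mentions a causal relationship with the treatment, and then describes signs and symptoms "whether or not related to the study assessment(s)/questionnaire(s").

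**The concern.** A causality item is useful in a randomised trial when it asks the same question about the randomised intervention in every subject. Here that intervention is an injection, and the one listed item asks about a device. Two raters could follow the protocol faithfully and code the same swollen wrist differently, one thinking of the debridement tool and the other of the PRP system.

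The plan itself foresees a PRP-specific harm: the risk list in section 11 includes an immune response to a component of PRP. Yet no listed item asks whether an event was related to the injection. The relatedness breakdown in section 9.3.4 is the only planned output that ties an AE to an intervention, because no breakdown by arm is listed. If its referent is unclear, or differs by arm, that breakdown cannot be interpreted. Causality is judged as events occur, and re-rating it later, possibly after unblinding, is weaker evidence.

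**Working it through.** The plan gives no figure on this point, so the check is to set each relevant statement beside the others and ask which injections it covers.

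| Section | Referent | Who is exposed | Covers PRP injection? | Covers saline injection? |
|---|---|---|---|---|
| 11 (AE form) | device, undefined | depends on reading | depends on reading | no, on either reading below |
| 6.2 | ArthroCare debridement tool | both arms, before randomisation | no | no |
| 12.3.3, read with 6.3 | study product, which would be the PRP system | PRP arm only | yes | no |
| 8.2 | the study | both arms | not specific | not specific |
| 11.1.1, first sentence | the treatment | both arms | plausibly | plausibly |
| 11.1.1, second sentence | assessments and questionnaires | both arms | no | no |
| 9.3.4 | none stated | not stated | not stated | not stated |

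Step 1: device means the debridement tool. The tool is used before randomisation, so exposure is the same in both arms. An injection reaction in either arm then has no listed item under which it can be called related.

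Step 2: device means the PRP system. A reaction after PRP can be rated related. The same reaction after saline cannot, because no PRP system was used. The criterion differs by arm, and a rater applying it literally has to know the allocation. Sections 4.1 and 4.5 blind medical staff outside the operating room. The documents do not say whether the person rating causality is blinded.

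Step 3: the other referents. Sections 8.2 and 11.1.1 use different words, and neither says how the form's item is to be rated. They show that the wording is unaligned, but they do not settle it.

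Step 4: an illustration of the mechanism. Assume the same number k of injection reactions in each arm of 24, an unblinded rater who calls every PRP-arm reaction related under Step 2, and a table split by arm. None of these is stated in the plan.

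- Truth: k/24 against k/24, difference 0.
- Step 1 reading: 0/24 against 0/24.
- Step 2 reading: k/24 against 0/24, so the apparent difference is k/24.

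For k = 5, 5/24 = 20.8%, so Step 2 would show 20.8% against 0%. Over the whole possible range, k = 0 gives 0/24 = 0% and k = 24 gives 24/24 = 100%. This shows the direction of the artefact and is not an estimate of its size.

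**The case against.** The strongest reply is that this is loose wording with little consequence. Several parts of that reply stand.

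- Section 11.1.1 says all reported AEs will be documented, and section 9.3.4 tabulates them overall, by severity and by preferred term. An injection reaction appears in those outputs however it is attributed.
- In a randomised trial, harm from the injection is shown mainly by comparing all AEs between arms, not by investigator attribution.
- Section 12.3.3 makes the study-product reading plausible, and on that reading PRP harm can be rated.
- Section 11.1.1 does mention the treatment. Its phrase about assessments and questionnaires is inclusive language about what counts as an AE and is not an instruction for rating causality.
- The form itself is not among the documents, and section 11 introduces its list with the word including, so the list may not be complete.

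A reader might infer that the relatedness table cannot show PRP harm at all. The documents do not support that: it requires device to mean the debridement tool, which they never say and which section 12.3.3 points away from. A reader might also infer that related events will appear in the PRP arm only. That requires an unblinded rater and a table by arm, and the plan states neither.

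The reply does not remove the core problem. No use of the word device in the plan can cover a saline injection, so the stated item does not fit the randomised comparison. The argument that comparison between arms does the real work exposes a further gap, because section 9.3.4 does not list arm.

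**Conclusion.** The concern holds in a limited form. The only causality item listed for AEs refers to an undefined device. Neither of the readings that the documents allow covers the saline injection, so relatedness to the randomised injection cannot be rated reliably or on equal terms in both arms. Capture and tabulation of the AEs themselves are not affected. The varied wording in sections 8.2 and 11.1.1, and the absence of arm from section 9.3.4, add to the problem. Without a breakdown by arm, the relatedness table could not compare the arms even with the right item.

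No numerical size can be given from the documents. The conclusion assumes that the form carries no further causality item beyond those section 11 lists. If the form already asks about the injection in both arms, what remains is to align the text and add arm to section 9.3.4. The change is worth making because it is cheap and alters what is recorded.

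**What to change.** 1. In section 11 and on the AE form, replace relationship to device with two items completed for every AE in both arms: relationship to the study injection (PRP or saline, in identical words for both arms) and relationship to the surgical procedure.
2. In section 9.3.4, state that relatedness means the study-injection item, and that AEs will be tabulated by treatment arm, both overall and within the breakdowns already listed.
3. Align sections 8.2 and 11.1.1 with the same referents, so that the study, the treatment, and the assessments and questionnaires are not used as though they were interchangeable.

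The cost is one form item reworded, one added, a few sentences of protocol text, and slightly more data entry per AE. Randomisation, visits and sample size are unchanged.

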#### Foreseeable Risk

- Discomfort
- Pain
- Redness
- Swelling
- Local or systemic infection
- Dehiscence and/or necrosis due to poor revascularization
- Specific or nonspecific immune response to some component of PRP treatment

### 11.1 DEFINITIONS

#### 11.1.1 ADVERSE EVENT

An adverse event (AE) is any untoward medical occurrence in a subject that does not necessarily have a causal relationship with the treatment. An adverse event can therefore be any unfavorable and unintended sign (including an abnormal laboratory finding), symptom, or temporal disease, whether or not related to the study assessment(s)/questionnaire(s).

Pre-existing disease or symptoms thereof prior to study enrollment are not considered AEs unless the condition recurs after the subject has recovered from the pre-existing condition, or the condition worsens in intensity or frequency during the study. Normal post-operative sequelae will not be recorded as adverse events. Specifically, normal post-operative pain, swelling, tenderness, loss of skin sensation and ecchymosis within the first two weeks postoperative, requiring normal levels of medication will not be recorded; all abnormal intensity or duration will be recorded and considered an adverse event as well as following the two-week post-operative period.

Adverse events will be monitored throughout the study. At each post-baseline visit, the Investigator will begin querying for adverse events by asking each subject a general, nondirected question such as "Have you had any changes to your condition since your last visit?" Previous adverse events and changes in therapy/concomitant medications should be updated. Directed questioning and examination will then be done as appropriate. All reported adverse events will be documented.

### 11.1.2 SERIOUS ADVERSE EVENT

A serious adverse event (SAE) is defined as any untoward medical occurrence that at any dose:

- results in death
- is life-threatening
- requires inpatient hospitalization or prolongation of existing hospitalization
- results in persistent or significant disability/incapacity
- is a congenital anomaly/birth defect

Important medical events that may not result in death, be life-threatening, or require hospitalization may be considered an SAE when, based upon appropriate medical judgment, they may jeopardize the subject or subject and may require medical or surgical intervention to prevent one of the outcomes listed in this definition.

### 11.2 PROCEDURES FOR REPORTING ADVERSE EVENTS

Adverse events should be reported to governing IRB per governing IRB reporting requirements.

### 11.3 REPORTING AN SAE

Any SAE occurring during the study period and for at least 30 days after the last study visit should be immediately reported (within 24 hours) and recorded. The Investigator should supply the Sponsor and the IRB with any additional requested information (e.g., hospital discharge summary, autopsy report, pathology report, operative report, terminal medical report, etc.).

## 12 ADMINISTRATIVE ISSUES

This protocol is to be conducted in accordance with the applicable Good Clinical Practice regulations and guidelines, e.g., the International Conference on Harmonisation (ICH) Guideline on Good Clinical Practice (GCP).

### 12.1 PROTECTION OF HUMAN SUBJECTS

### 12.1.1 COMPLIANCE WITH INFORMED CONSENT REGULATIONS

Written informed consent is to be obtained from each subject prior to enrollment into the study, and/or from the subject's legally authorized representative. The process for obtaining informed consent must also be documented in the subject's medical record.

### 12.1.2 COMPLIANCE WITH IRB REGULATIONS

This study is to be conducted in accordance with applicable IRB regulations. The Investigator must obtain approval from a properly constituted IRB prior to initiating the study and re-approval or review at least annually.

### 12.1.3 COMPLIANCE WITH GOOD CLINICAL PRACTICE

This protocol is to be conducted in accordance with the applicable GCP regulations and guidelines.

## 12.2 SUBJECT CONFIDENTIALITY AND PRIVACY

A report of the results of this study may be published, but the subject's name will not be disclosed in these documents. The subject's name may be disclosed to the study Sponsor, the governing health authorities or the Food and Drug Administration (FDA), if they inspect the study records. Appropriate precautions will be taken to maintain confidentiality of medical records and personal information.

Written Authorization and other documentation in accordance with the relevant country and local privacy requirements (where applicable) are to be obtained from each subject prior to enrollment into the study, and/or from the subject's legally authorized representative in accordance with the applicable privacy requirements (e.g., HIPAA).

## 12.3 DOCUMENTATION

### 12.3.1 SOURCE DOCUMENTS

Source documents may include a subject's original (or certified copy) medical records, hospital charts, clinic charts, the Investigator's subject study files, as well as the results of diagnostic tests such as X-rays and MR Arthrograms.

The following information should be entered into the subject's medical record:

- Subject's name
- Subject's contact information
- Date that the subject entered the study and subject number
- The study title and/or the protocol number
- A statement that informed consent was obtained and the process for obtaining consent, including the date. A statement that HIPAA Authorization or other country and local subject privacy required documentation for this study has been obtained, including the date.
- Dates of all subject visits
- All concomitant procedures
- Subject standardized radiology as specified in the outcome metrics
- Occurrence, treatment for, and status of any adverse events
- Date the subject exited the study, and a notation as to whether the subject completed the study or reason for discontinuation.
- Protocol deviations, as applicable

---

#### 12.3.2 DOCUMENT COMPLETION

Source documents must meet the criteria to be acceptable in assessing the quality and integrity of the data during inspection or review of that data: attributable, legible, contemporaneous, original, accurate and available upon request. The Investigator is responsible for ensuring that data is properly recorded on each subject's record.

---

#### 12.3.3 RETENTION OF DOCUMENTATION

All study related correspondence, subject records, consent forms, subject privacy documentation, records of the distribution and use of device, and copies of documentation should be maintained on file. Documents should be retained and available for audit by regulatory authorities until at least 2 years after the latest among the following scenarios: completion or termination of the study, the last approval of a marketing application, no pending or contemplated marketing applications, or formal discontinuation of clinical development of the device. These documents should be retained for a longer period, however, if mandated by the applicable regulatory requirements, by conditions imposed by the IRB.

